8.9 Pharmacodynamics

Not applicable.

8.10 Interim analysis

Two administrative interim analyses will be conducted. The first one is planned after at least 45 patients have performed their CFVR measurement at Visit 4 and the second after at least 100 patients have performed their CFVR measurement at Visit 4. The variables for the analyses will be:

- CFVR
- LV Global Longitudinal Strain (GLS) at rest
- LVEF
- Carotid-femoral pulse wave velocity and brachial pulse wave analysis: Augmentation index, Carotid-femoral pulse wave velocity, Pulse pressure amplification and Central pulse pressure
- Cardiovascular Biomarkers: hsCRP (High-sensitivity C-Reactive Protein), NT-proBNP (N-Terminal Prohormone of Brain Natriuretic Peptide)

These analyses will not have any impact on the overall type-1 error because no changes will be made to the trial based on the outcome of the analyses. The purpose with the interim analyses is to trigger external activities not connected to the trial. Both interim analyses will be performed by study independent personnel.

An Interim Analysis Charter will define the deliverables and procedures for the provision and communication of the planned interim analyses described in the statistical analysis plan. The maintenance of the blind for the Study Team is also addressed. Further details will be given in the Interim Analysis Charter.

The two interim analyses will be focused on to:

Description of the study population:

- Description and comparison of the active groups and the placebo group
- Estimation of the effect on safety variables

The cut-off date for second IA will be determined by the study team.

8.10.1 Description of study population

In order to characterize the population used for the interim analyses, subject disposition, important protocol deviations and analysis sets will be presented.

Distribution:

Original:

Copy:

TPCA025 Version 2 (based on TPQA036 Version 2)

Sponsor:	AstraZeneca AB	Protocol/CIP Number:	D7550C00003
CIL Project Number:	40343		

Subject disposition

Subject disposition - Cohort 4w treatment and Cohort 12w treatment - and analysis sets will be summarized.

Additionally, for the second IA, the demographic characteristics will be presented by cohort of patients and will include Age (years), Age group (<50; >=50 -<65; >=65 years), sex, race, ethnicity and country.

Important protocol deviations

IPDs are described and classified section 8.2.

Classified IPDs will be assessed for the Efficacy Analysis Set. The number and percentage of subjects with at least one IPD will be summarized globally and for each category, by treatment group and total.

8.10.2 Description and comparison of the active groups and the placebo group

First IA

The comparison will be performed on change from baseline at Visit 4 in

- CFVR
- LV Global Longitudinal Strain (GLS) at rest
- LVEF
- Carotid-femoral pulse wave velocity and brachial pulse wave analysis: Augmentation index, Carotid-femoral pulse wave velocity, Pulse pressure amplification and Central pulse pressure
- Cardiovascular Biomarkers: hsCRP (High-sensitivity C-Reactive Protein), NT-proBNP (N-Terminal Prohormone of Brain Natriuretic Peptide)

The comparison will be based on the Efficacy Analysis Set.

For additional details on these variables see sections $6.4.2, \underline{6.9.1}$ and $\underline{6.8}$.

The change from baseline for

- CFVR
- LV Global Longitudinal Strain (GLS) at rest
- LVEF
- Carotid-femoral pulse wave velocity and brachial pulse wave analysis: Augmentation index, Carotid-femoral pulse wave velocity, Pulse pressure amplification and Central pulse pressure

will be analysed using the ANCOVA model described in section 7.1 with data from visit 2, and 4.

The change from baseline for

Distribution:

Original:

Copy:

TPCA025 Version 2 (based on TPQA036 Version 2) Effective Date: 27th August 2017 Prior Effective Date: 21st December 2016

Sponsor:	AstraZeneca AB	Protocol/CIP Number:	D7550C00003
CIL Project Number:	40343		

 Cardiovascular Biomarkers: hsCRP (High-sensitivity C-Reactive Protein), NT-proBNP (N-Terminal Prohormone of Brain Natriuretic Peptide))

will be analysed using the MMRM model described in section 7.1 with data from visit 2, 3 and 4.

CFVR is log-Normal distributed. The analysed change from Baseline is calculated as Visit value in log minus the Baseline value in log. The reportable results will be those for log-Normal variables.

All the other variables will be firstly tested for Normality (Normality will be evaluated using Q-Q plots). If the distribution appears to be Normal, the analysed change will be the Visit value minus the Baseline value. The reportable results will be those for Normal variables. If the distribution appears to be log-Normal, the analysed change will be the Visit value in log minus the Baseline value in log. The reportable results will be those for log-Normal variables.

Two-sided test will be used to compare the change from baseline observed in the active group, vs the change from baseline observed in the placebo group. Alpha level will be set at 0.05. Comparison of AZD5718 versus placebo will also be assessed within the same model.

For further details on the model please refer to Appendix 2 and to the table in Appendix 3.

In addition to the results above, also descriptive statistics will be reported by group for the actual value and for the change from baseline; descriptive statistics will be reported for all visits up to visit 4.

Second IA

The comparison will be performed on change from baseline at Visit 4 and Visit 4c in

- CFVR
- LAD hyperaemic flow velocity
- LV Global Longitudinal Strain (GLS) at rest
- LVEF
- Cardiovascular Biomarkers: hsCRP (High-sensitivity C-Reactive Protein), NT-proBNP (N-Terminal Prohormone of Brain Natriuretic Peptide)

The comparison will be based on the Efficacy Analysis Set.

For additional details on these variables see sections $6.4.2, \underline{6.9.1}$ and $\underline{6.8}$.

The change from baseline for

- CFVR
- LAD hyperaemic flow velocity
- LV Global Longitudinal Strain (GLS) at rest
- LVEF

Distribution:

Original:

Copy:

TPCA025 Version 2 (based on TPQA036 Version 2)

Sponsor:	AstraZeneca AB	Protocol/CIP Number:	D7550C00003
CIL Project Number:	40343		

will be analysed using the MMRM model described in section 7.1 with data from visit 2, 4 and 4c for both comparisons (Visit 4 and Visit 4c).

The change from baseline for

 Cardiovascular Biomarkers: hsCRP (High-sensitivity C-Reactive Protein), NT-proBNP (N-Terminal Prohormone of Brain Natriuretic Peptide))

will be analysed using the MMRM model described in section 7.1 with data from visit 2, 3, 4 and 4c for both comparisons (Visit 4 and Visit 4c).

CFVR is log-Normal distributed. The analysed change from Baseline is calculated as Visit value in log minus the Baseline value in log. The reportable results will be those for log-Normal variables.

All the other variables will be firstly tested for Normality (Normality will be evaluated using Q-Q plots). If the distribution appears to be Normal, the analysed change will be the Visit value minus the Baseline value. The reportable results will be those for Normal variables. If the distribution appears to be log-Normal, the analysed change will be the Visit value in log minus the Baseline value in log. The reportable results will be those for log-Normal variables.

Two-sided test will be used to compare the change from baseline observed in the active group, vs the change from baseline observed in the placebo group. Alpha level will be set at 0.05. Comparison of AZD5718 versus placebo will also be assessed within the same model.

For further details on the model please refer to Appendix 2 and to the table in Appendix 3.

In addition to the results above, the following will be reported:

- Descriptive statistics by group for the actual value and for the change from baseline; descriptive statistics for all visits up to visit 4c;
- Graphical representations of change from baseline (mean(SD)) over time and by groups;
- Forest plots based on the results of the two models.

8.10.3 Estimate the effect on safety variables

The effect on safety variables will be presented using the Safety Analysis Set by treatment group. Below a detailed description of the summaries that will be used for the purpose:

Adverse Events

AEs will be assigned to the study phases as described in section 6.6.2.

Original:

Copy:

TPCA025 Version 2 (based on TPQA036 Version 2) Effective Date: 27th August 2017 Prior Effective Date: 21st December 2016

Sponsor:	AstraZeneca AB	Protocol/CIP Number:	D7550C00003
CIL Project Number:	40343		

Unless otherwise specified, AEs and SAEs will be summarized using the Safety Analysis Set by treatment group and by cohort of patients. Percentages will be based on the total numbers of subjects in the treatment group.

Subjects with multiple events in the same category will be counted only once in that category. Subjects with events in more than 1 category will be counted once in each of those categories.

Only On-treatment phase up to visit 4 at the first IA and up to the cut-off date at the second IA will be reported for each summary table.

The following summary tables will be reported:

An overview table for all the AEs, only for the On-treatment phase.

The number and percentage of subjects with any AEs for each SOC and PT, only for the On-treatment phase.

The number and percentage of subjects with any SAEs for each for each SOC and PT, only for the On-treatment phase.

The following table will be reported for the first IA only:

The number and percentage of subjects with any non-serious AEs only for the On-treatment phase and only for those categories which show more that 5% of frequency, globally and for each PT.

Additionally, for the second IA, the following summary tables will be reported:

The number and percentage of subjects with AEs with outcome of death for each SOC and PT, only for the On-treatment phase.

The number and percentage of subjects with AEs leading to treatment discontinuation for each SOC and PT in the On-treatment phase.

The following listings will be reported for the second IA:

Listings will also be presented by subject for all AEs using the Safety Analysis Set.

Listing of SAEs will also be presented for enrolled but not randomized subjects and for subjects who were not exposed to treatment.

Laboratory test results for haematology, coagulation and clinical chemistry

Clinical laboratory evaluation is performed based on the Safety Analysis Set. The list and the assessment of all Clinical Laboratory variables are reported section 6.6.3.

Distribution:

Original:

Copy:

TPCA025 Version 2 (based on TPQA036 Version 2)

Sponsor:	AstraZeneca AB	Protocol/CIP Number:	D7550C00003
CIL Project Number:	40343		

Laboratory test results for haematology, coagulation and clinical chemistry will be summarized in AZ preferred units for each treatment group, and for change from baseline at each visit up to visit 4 at the first IA and up to visit 4c at the second IA.

Additionally, for the second IA the following tables will be produced:

Classification of the laboratory values with respect to the normal reference range will be provided (low/normal/high). Shifts from baseline to maximum/minimum value during Ontreatment phase of this classification will be presented for each treatment group and by cohort of patients.

Hy's law criteria will also be summarized in a double-entry table by cohort of patients.

Laboratory test results for urinalysis

Laboratory test results for quantitative variables (i.e. creatinine and albumin) will be summarized in AZ preferred units for each treatment group, and for change from baseline at each visit. Change from baseline to each post-baseline visit will be calculated as the post-baseline visit value minus the baseline visit value. Only data up to visit 4 at the first IA and up to visit 4c at the second IA will be presented.

Shifts from baseline to maximum value during On-treatment phase will be presented for semi-quantitative urinalysis variables (i.e. albumin, protein, blood, glucose and Leukocytes). Only On-treatment phase up to visit 4 at the first IA and up to visit 4c at the second IA will be used for each summary table.

All laboratory data for urinalysis will be also presented in listing.

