1.3 Benefit/risk and ethical assessment

AZD5718 has been administered to 84 healthy subjects (in completed studies or studies in reporting phase) in single doses up to 1200mg, and in repeated doses up to 600 mg for 10 days. The compound has been well tolerated in healthy subjects. No clinically meaningful differences for changes over time in clinical laboratory tests, vital signs or electrocardiograms (ECGs) were observed between subjects who received AZD5718 and those who received placebo. There were no deaths or serious adverse events (SAEs) and all subjects completed the studies. The most common adverse event (AE) was headache. No safety concerns were raised during the studies.

Preclinical safety studies have identified several potential risks including transaminase elevations, pharyngeal and gastric mucosal lesions and delayed gastric emptying, plasma glucose elevation, minimal hypertrophy of thyroid follicular cells and potential effects on heart rate and blood pressure. None of these findings were observed in the clinical studies performed to date. The preclinical safety findings are described in more detail in the Investigators Brochure.

Based on knowledge of the mechanism of action, previous clinical experience and the preclinical safety studies the potential risks will be closely monitored. No specific harms are anticipated from participating to this trial. Available preclinical and clinical data suggest that the subjects may benefit from participation in the study as inhibition of 5-LO pathway may improve coronary microvascular function, reduce coronary artery plaque progression and

improve left ventricle ejection fraction. Based on prior SMAD study, the effect of AZD5718 can be detected in decreased u-LTE₄ concentrations under the designed 4 weeks of study treatment period, though potentially reaching even more stable and sustainable effect with the treatment prolongation up to 12 weeks.

The extended treatment period up to 12 weeks, will also provide with more complete safety profile data in CAD patients (post-ACS population) with longer treatment exposure.

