6.3.6 Adverse events based on examinations and tests

The results from the CSP mandated laboratory tests and vital signs will be summarised in the CSR. Deterioration as compared to baseline in protocol-mandated laboratory values, vital signs should therefore only be reported as AEs if they fulfil any of the SAE criteria or are the reason for discontinuation of treatment with the IP.

If deterioration in a laboratory value/vital sign is associated with clinical signs and symptoms, the sign or symptom will be reported as an AE and the associated laboratory result/vital sign will be considered as additional information. Wherever possible the reporting Investigator uses the clinical, rather than the laboratory term (e.g., anaemia versus low haemoglobin value). In the absence of clinical signs or symptoms, clinically relevant deteriorations in non-mandated parameters should be reported as AE(s).

If clinically non-significant ECG findings are reported they are not required to be recorded as AEs, unless there are clinical symptoms and actions taken that merit for AE/SAE reporting on their own.

Any new or aggravated clinically relevant abnormal medical finding at a physical examination as compared with the baseline assessment will be reported as an AE.

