8.5.6 Interim analysis

Two administrative interim analyses will be conducted. The first one is planned after at least 45 patients have performed their CFVR measurement at Visit 4 and the second after at least 100 patients have performed their CFVR measurement at Visit 4. The variables for the analyses will be CFVR and LV Global Longitudinal Strain (GLS). These analyses will not have any impact on the overall type-1 error because no changes will be made to the trial based on the outcome of the analyses. The purpose with the interim analyses is to trigger external activities not connected to the trial. Both interim analyses will be performed by study independent personnel.

The models for the interim analysis will be analysed using Analysis of Covariance with treatment, type of MI (STEMI vs NSTEMI) and baseline value as covariates, with compound symmetry as covariance structure. Change from baseline will be used as endpoint and the analysis will be done on loge scale. The result will be back transformed to original scale.

For the second interim analysis, all data available will be used to measure change from baseline in a repeated measures model with treatment, type of MI, time (from randomization) and treatment*time interaction as fixed effects, baseline value will be used as covariate. The exact model will be prespecified in the interim analysis plan. Change from baseline will be used as endpoint and the analysis will be done on loge scale. The result will be back transformed to original scale

In the event of positive outcome at any of the administrative interim analyses an evaluation of exposure-response relationship may be performed. This analysis has the intention to guide the dose setting for the next study. This will be performed by non-study personnel with no other involvement in the study. Data for this analysis will be based on PK, u-LTE₄ and CFVR.

In connection to the first administrative interim analysis, a safety review committee (SRC) will be unblinded to safety data including AEs, SAEs and safety labs to ensure no safety concerns are associated with AZD5718 treatment.

An interim analysis plan will be prepared and finalized prior to the first administrative interim analysis. A separate analysis plan will also be prepared for the evaluation of exposure-response relationship and it should be finalised prior to the first administrative interim analysis

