- Protocol section 8.3.1 stated that the efficacy analysis set will include all patients who were randomised, received at least one dose of study medication and have at least one baseline or postbaseline measurement. However, here it will have specified that this population will include all patients who were randomised, received at least one dose of study medication and have at least one baseline or postbaseline measurement for at least one of the efficacy variables (including all, primary secondary or exploratory variables).
- Protocol section 8.5.6 stated that an interim analysis plan will be prepared and finalized prior to the first administrative interim analysis. However, this interim analysis plan is based on a dedicated section of the SAP and there will be an update of the interim analysis charter before the second interim analysis.
- Protocol section 8.1 stated that any subsequent amendments to the SAP will be documented, with final amendments completed prior to unblinding of the data for the analysis. But it should be added that unblinded team will not be involved in any SAP amendment which will take place after the first unblinding for the first interim analysis.
- Protocol section 4.1 stated that CFVR measurement should be done before the IP intake during the visit. In the SAP, measurements done 3 days after last dose can be considered as the visit measurement.
- Protocol section 5.3.2 included a brief description of the question SF-36 V1 while V2 is used in the study. The wording was updated in the SAP to be consistent with the questionnaire SF-36 V2.

Distribution:

Original:

Copy:

TPCA025 Version 2 (based on TPQA036 Version 2) CONFIDENTIAL AND PROPRIETARY

Page 17 of 80

Sponsor:	AstraZeneca AB	Protocol/CIP Number:	D7550C00003
CIL Project Number:	40343		

- Protocol section 2.2 stated that standard model population PK parameters would be reported in a separate report. However, plasma concentrations will be part of the CSR and PK parameters described in a separate report.
- Protocol section 4.1 described an on-site Visit 5 (Follow-up). However, due to COVID19 situation, some phone visits replaced on-site visits. Protocol deviations were reported for each patient in that situation.

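### The safety tables listed for the first interim, the one tied to the unblinded Safety Review Committee, omit vital signs and ECG and give only a limited liver view

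*SAP*

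**What the plan says.** Protocol 2.3 sets four safety outcome measures: adverse events, vital signs, chemistry and haematology, and ECG. Protocol 1.3 lists risks found in preclinical work, among them transaminase elevations and "potential effects on heart rate and blood pressure", and commits to close monitoring of them.

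Protocol 8.5.6 plans two administrative interims. On the first: "The first one is planned after at least 45 patients have performed their CFVR measurement at Visit 4". The committee is attached to that look: "In connection to the first administrative interim analysis, a safety review committee (SRC) will be unblinded to safety data including AEs, SAEs and safety labs". No committee review is tied to the second interim.

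SAP 5.2 states that "this interim analysis plan is based on a dedicated section of the SAP"; the same sentence foresees an update of the interim charter before the second interim. SAP 8.10.3 opens its safety list with "Below a detailed description of the summaries that will be used for the purpose". Under the blood laboratory heading it adds, before the reference-range shifts and the Hy's law table: "Additionally, for the second IA the following tables will be produced".

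Protocol 6.3.6 limits what reaches the AE tables. Deteriorations in protocol-mandated laboratory values and vital signs "should therefore only be reported as AEs if they fulfil any of the SAE criteria or are the reason for discontinuation" of treatment. Associated clinical signs or symptoms are still reported as AEs.

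**The concern.** The SRC's task at the first interim is to establish that the drug raises no safety concern. The patients start treatment 7 to 28 days after an acute coronary syndrome, and the human repeat-dose experience summarised in Protocol 1.3 is 10 days in healthy subjects. Heart rate and blood pressure are risks the protocol itself names, yet the tables listed for this interim do not compare them between arms. The AE reporting rule means that a modest, symptom-free shift would not surface as events. If the SRC received only the listed tables, its opinion would carry no by-arm evidence on the haemodynamic risk and only coarse evidence on the liver.

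**Working it through.** The point is about which tables are listed, so there is no stated figure to reproduce. The check sets the sections side by side.

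**1. Coverage of the Protocol 2.3 outcome measures**

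| Measure | First interim (SAP 8.10.3) | Second interim (SAP 8.10.3) | Final analysis |
|---|---|---|---|
| AEs/SAEs | Overview; AEs and SAEs by system organ class and preferred term; non-serious AEs above 5% | First three of these, plus deaths, AEs leading to discontinuation, listings | Full set (8.8.2) |
| Blood laboratory | Values and change by visit to Visit 4 | To Visit 4c, plus reference-range shifts and ALT/AST by bilirubin | All of these (8.8.3) |
| Vital signs | None | None | By visit, by arm (8.8.4) |
| ECG | None | None | Shift in overall rating (8.8.4) |

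Urinalysis summaries and shifts are given at both interims. Two of the four measures have no table at the first interim, or at the second.

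**2. Can the AE tables fill the vital-sign gap?** Only in part. Under Protocol 6.3.6 a serious deterioration, one that stops treatment, or one with symptoms can reach them. A symptom-free, non-serious change that does not stop treatment cannot. ECG is less closed, because Protocol 5.2.4 lets clinically significant abnormalities be recorded as AEs.

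**3. Can another first-interim output fill it?** SAP 8.10.2 compares central pulse pressure and pulse pressure amplification by arm, as efficacy variables. Pulse pressure is systolic minus diastolic (S − D). If both fall by d, then (S − d) − (D − d) = S − D, so a parallel shift cancels. Amplification is a ratio of two such differences (SAP 6.9.1). Neither contains heart rate or shows the level of blood pressure.

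**4. What is visible for the liver?** SAP 7.1 summaries include the maximum, so the highest ALT, AST and bilirubin per arm and visit would be shown. Potential Hy's Law cases are reported as SAEs (Protocol Appendix D, 4.2) and reach the SAE table. What is missing is the per-patient grading in SAP 6.6.3 (3 to <5, 5 to <10 and ≥10 xULN, using the highest on-treatment value). A mean conceals a single case: one patient rising by 2 xULN moves the arm mean by 2/18 = 0.11 xULN, or 2/9 = 0.22 xULN in the smaller arm. The maximum reveals that patient, but one maximum per arm and visit cannot distinguish one raised patient from several.

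**5. Size of the first look**
- Patients: 45 (minimum, Protocol 8.5.6), allocated 2:1:2 (SAP 4.3). 45 × 2/5 = 18; 45 × 1/5 = 9; 45 × 2/5 = 18.
- Vital signs are scheduled at Visits 2, 3 and 4 in this span (Protocol Table 1): 45 × 3 = 135 patient-visits.
- All day 1 vital signs count as baseline (SAP 6.2.2), so Visit 2 contributes 45 baseline records. Post-baseline: 135 − 45 = 45 × 2 = 90, that is 36/18/36 by arm, assuming full attendance.

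**The case against.** The strongest reply is that SAP 8.10.3 is not shown to be the SRC's package. It describes outputs for administrative interims meant to inform activities outside the trial. Protocol 8.5.6 introduces the SRC's data with an open-ended word, and SAP 8.10 says a charter will define the deliverables. That stands: the charter is not supplied, and it may already provide vital signs.

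It is also fair that the SAP delivers what Protocol 8.5.6 names, so those two sections do not conflict. Close monitoring can be read as the per-visit measurements, on-site ECG reading and the sponsor's continuing surveillance. But none of those supplies an unblinded comparison between arms, which is what the SRC look is for. The ECG table would add little, because SAP 5.2 reduces ECG to the investigator's overall rating.

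A reader might infer something stronger: that the SRC cannot see the risks the protocol names, or that no one else unblinded could. The documents do not support that.
- Liver tests, glucose and thyroid tests are in the summarised chemistry panel.
- Appendix D requires notification of the sponsor for any ALT or AST at or above 3 xULN.
- Symptomatic haemodynamic changes and clinically significant ECG findings can reach the AE tables.
- SAP 6.4.1 describes dedicated unblinded teams, so the SRC is not the only unblinded party.

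**Conclusion.** The point holds in a limited form. As written, the first-interim list contains no by-arm vital-sign or ECG output. It reserves the blood-laboratory shift, ALT/AST-by-bilirubin and discontinuation-AE tables for the second interim. The clear gap is a symptom-free, non-serious shift in pulse or blood pressure, which none of the listed tables would show, although about 90 post-baseline patient-visits would be on file. The liver gap is one of resolution.

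This rests on two assumptions: that SAP 8.10.3 is followed as written, and that the charter adds nothing to it. What the SRC was actually given cannot be established from the documents. The point does not affect the efficacy analyses or the type I error. It is worth changing because the remedy is cheap and the omitted measures include a named cardiovascular risk.

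**What to change.** In SAP 8.10.3:
1. Add Table 14.3.8.1 (vital signs over time) to the first-interim package. This is the main change.
2. Add the ECG shift tables, 14.3.8.4 and 14.3.8.5.
3. Produce at both interims the blood-laboratory shift tables (14.3.7.2 to 14.3.7.5), ALT/AST by bilirubin (14.3.7.8 and 14.3.7.9) and AEs leading to discontinuation (14.3.5.1).

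In Protocol 8.5.6, extend the SRC's data to AEs, SAEs, safety labs, vital signs and ECG, and make the charter agree. If the charter already supplies these outputs, a cross-reference in the SAP is enough. If the first interim has already run, produce the tables on the same data cut and document what the SRC saw.

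The cost is wording in the SAP, protocol and charter, and a small amount of extra programming by the unblinded team. All these tables are already specified for the final analysis, so no new data, visits or patients are needed.
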